3. OBJECTIVES

Our primary objectives are to:

- Describe the epidemiology, clinical presentation, bleeding score, bleeding episodes, quality of life, laboratory parameters, genetics and treatment of *homozygous* and known *heterozygous* individuals (of all ages) with rare bleeding disorders (disorders of fibrinogen, FII, FV, FV & VIII, FVII, FX, FXI, FXIII, alpha-2-antiplasmin and PAI-1 deficiency) in the Netherlands;
- Examine the relationship between the clinical and laboratory presentation (clinical and laboratory phenotype), and between phenotypes and genetics (genotype);
- Examine the relationship between quality of life, phenotype and genotype;
- ~~Validate the established factor activity levels for patients to remain without symptoms.~~

Our secondary objectives are to:

- Validate the established factor activity levels for patients to remain without symptoms.
- Compare the clinical presentation, bleeding score, quality of life and laboratory parameters of individuals with a rare bleeding disorder (disorders of fibrinogen, FII, FV, FV & VIII, FVII, FX, FXI, FXIII, alpha-2-antiplasmin and PAI-1 deficiency) to those of individuals with haemophilia A or B in cooperation with the HIN-6 investigators
- Establish a firm base for a future Dutch registry for *homozygous* and known *heterozygous* individuals with rare bleeding disorders
 - To develop a standard set of patient-reported, clinical and administrative data to be collected on a regular basis
- Liaise with the pro-RBDD study, a similar study in Italy, to work towards a pan-European study linking phenotype to genotype in individuals with rare bleeding disorders
- To assess if the NHA can distinguish mild clinical phenotypes in patients with similar factor activity levels
- To evaluate the usefulness of saliva coagulation biomarker tests in the management of patients with a rare bleeding disorder
- To examine whether age-dependent laboratory changes in factor concentrations and fibrinolysis occur in individuals with rare bleeding disorders and if so, whether they influence clinical phenotype
- To evaluate if patients with rare bleeding disorders are protected from arterial thrombosis

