7. STATISTICAL ANALYSIS

Statistical analysis will be performed by the research team at Radboud university medical center. First we describe the general outline of statistical analyses, then we discuss specific statistical procedures for the primary and secondary objectives separately, if appropriate.

In general, continuous variables will be described using standard summary statistics (e.g. mean, medians and corresponding 95% confidence interval (CI),); categorical variables will be described using frequencies and percentages with their 95% CIs. Group differences will be determined using analysis of variance (ANOVA) or Student's t-test for continuous variables and Fisher's exact test for categorical variables (Fisher-Freeman-Halton exact test for variables with more than two categories). Non-parametric tests will be used for results with non-normal distributions. Two-sided p-values smaller than 0.05 will be considered statistically significant. Because of the explorative character of this study no correction for multiple testing will be applied.

The following parameters will be categorized when appropriate:

- Bleeding score (ISTH-BAT): ≥ 5 abnormal for women, ≥ 3 abnormal for men
- Clinical bleeding severity [19]:
 - Asymptomatic: no documented bleeding episodes
 - Grade I bleeding: bleeding that occurred after trauma or drug ingestion (antiplatelet or anticoagulation therapy)
 - Grade II bleeding: spontaneous minor bleeding (bruising, ecchymoses, minor wounds, oral cavity bleeding, epistaxis and menorrhagia)
 - Grade III bleeding: spontaneous major bleeding (intramuscular haematomas requiring hospitalizations, haemarthrosis, bleeding of the central nervous system, the umbilical cord or the gastrointestinal tract)

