7.2. Secondary objectives

- *Compare the clinical presentation, bleeding score, quality of life and laboratory parameters of individuals with a rare bleeding disorder (disorders of fibrinogen, FII, FV, FV & VIII, FVII, FX, FXI, FXIII and alpha-2-antiplasmin and PAI-1 deficiency) to those of individuals with haemophilia A or B (HiN study data will be shared)*
Descriptive statistics will be used. Group differences will be determined using the statistics as described in Statistical Analysis above.
- *Establish a firm base for a future Dutch registry for homozygous and known heterozygous individuals with rare bleeding disorders (disorders of fibrinogen, FII, FV, FV & FVIII, FVII, FX, FXI, d FXIII and alpha-2-antiplasmin and PAI-1 deficiency):*
 - *To develop a standard set of patient-reported, clinical and administrative data to be collected on a regular basis*

No statistics are involved in this objective.

- *Liaise with the pro-RBDD study, a similar study in Italy, to work towards a pan-European study linking phenotype to genotype in individuals with rare bleeding disorders*
No statistics are involved in this objective.
- *To assess if the NHA can distinguish mild clinical phenotypes in patients with similar factor activity levels*
We will calculate diagnostic accuracy comparing NHA to ISTH BAT.
- *To evaluate the usefulness of saliva coagulation biomarker tests in the management of patients with a rare bleeding disorder*
Descriptive statistics will be used. Regression analysis will be used to determine the association between saliva biomarker tests (dependent variable) and coagulation factor activity level as a continuous variable (independent variable), with adjustment for age at data collection, sex, etcetera.

- *To evaluate the use of WES in explaining differences in bleeding tendency.*
Descriptive statistics will be used.
- *To examine whether age-dependent laboratory changes in factor concentrations and fibrinolysis occur individuals with rare bleeding disorders? And if so, do they influence clinical phenotype?*
Descriptive statistics will be used. Regression analysis will be used to determine the association between age (dependent variable) and coagulation factor activity level as a continuous variable (independent variable), with adjustment for age at data collection, sex, etcetera.
- *To evaluate if patients with rare bleeding disorders are protected from arterial thrombosis*

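### Section 7 leaves open whether ISTH-BAT group comparisons use the full score or the normal/abnormal cut, and none of its group tests accounts for sex

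*Combined protocol and SAP*

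**What the plan says.** Section 7 introduces a short list with "The following parameters will be categorized when appropriate". Its first entry is "Bleeding score (ISTH-BAT): ≥ 5 abnormal for women, ≥ 3 abnormal for men". No analysis is named in which this two-class version is to be used.

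The tests come just before that list: "Group differences will be determined using analysis of variance (ANOVA) or Student's t-test for continuous variables and Fisher's exact test for categorical variables". The section adds "Non-parametric tests will be used for results with non-normal distributions" and "Two-sided p-values smaller than 0.05 will be considered statistically significant". It applies no multiplicity correction.

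Among the secondary objectives in section 3 is to "Compare the clinical presentation, bleeding score, quality of life and laboratory parameters of individuals with a rare bleeding disorder" with those of people with haemophilia A or B. For that objective section 7.2 says only "Group differences will be determined using the statistics as described in Statistical Analysis above", so the choice of scale is passed back to section 7.

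Elsewhere the plan is more definite. The first primary objective in section 7.1, which includes the bleeding score, is described with means, SDs and medians. The regressions in section 7.1 treat clinical bleeding severity as continuous and adjust for age and sex. The group-difference tests in section 7 have neither feature.

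**The concern.** Two gaps meet in the same comparison.

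**Scale.** The limit separates normal from abnormal bleeding, but everyone compared has an established bleeding disorder. The protocol itself expects known heterozygous patients to be the more severe subset (section 5.1) and notes that clinical records favour patients with more severe bleeding (section 1.2). Many patients on both sides are therefore likely to lie above the limit, where a two-class variable cannot distinguish them. Section 2 wants to know whether rare bleeding disorders really are milder than haemophilia, and much of the relevant difference may lie there. Because the scale is not fixed, it can also be chosen after the data are seen, with no multiplicity correction.

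**Sex.** Different limits for women and men imply that scores differ by sex. If the groups also differ in sex mix, a test that ignores sex mixes the two effects, on either scale.

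All known patients are already invited and there is no replacement (sections 5.1 and 6.4), so lost information cannot be made good by recruiting more.

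**Working it through.** The documents give no power, effect size or ISTH-BAT distribution, so there is no planned figure to reproduce. Everything below is conditional on the stated assumptions.

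**Group sizes.** Table 3 count × 0.70 (expected response, section 5.1): FVII 92 × 0.70 = 64.4; FXI 88 × 0.70 = 61.6; PAI-1 39 × 0.70 = 27.3; alpha-2-antiplasmin 29 × 0.70 = 20.3; fibrinogen 28 × 0.70 = 19.6.

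**Tests compared, two-sided 5%.**
- Fisher's exact test on score ≥5 (women) / ≥3 (men).
- Sex-stratified Wilcoxon (van Elteren) on the full score: Z = Σ w(W − E[W]) / √Σ w²Var(W), summed over the two sexes, with w = 1/(N+1), where W is the rank sum of one group and N the number of patients of that sex.

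**1. Similar sex mix.** Assumed: negative binomial scores with dispersion k, half women in each group, women's means 1.25 times men's, a true 1.5-fold difference in mean. FVII v FXI (64 v 62), 3,000 runs per setting:

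| Male means | k | Fisher on cut | Stratified Wilcoxon | Loss (points) |
|---|---|---|---|---|
| 4 v 6 | 3 | 56% | 84% | 28 |
| 6 v 9 | 3 | 41% | 87% | 46 |
| 8 v 12 | 3 | 28% | 90% | 62 |
| 4 v 6 | 1.5 | 39% | 60% | 21 |
| 6 v 9 | 1.5 | 29% | 62% | 33 |
| 8 v 12 | 1.5 | 24% | 65% | 41 |

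Fibrinogen v FVII (20 v 64): 14–29% against 31–61%. PAI-1 v alpha-2-antiplasmin (27 v 20): 7–20% against 24–46%. With no true difference, the stratified test rejected in 4.6–5.5% of runs. The smallest loss in any of these scenarios was about 10 points.

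**2. A different model.** Normal scores, standardised difference d = 0.5, t-test on the full score against exact enumeration of Fisher's test, 64 v 62. If a share p of the milder group lies above the limit, the share in the other group is Φ(Φ⁻¹(p) + 0.5); for p = 0.70 this is Φ(0.524 + 0.5) = 0.85. Power on the full score is 79.5%. On the cut it is 58.6%, 46.4%, 35.6% and 16.9% for p = 0.5, 0.7, 0.8 and 0.9, a loss of 21, 33, 44 and 63 points. Over a wider grid (d from 0.3 to 0.8, groups from 7 to 200) the loss runs from 1 to 87 points. It is small where power is near its floor or near 100%.

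**3. Fewer scored patients.** Table 4 lists iCHEC for children, and about one third of known patients are minors (section 8.4). If only adults have ISTH-BAT, 64 × 2/3 ≈ 43 and 62 × 2/3 ≈ 41. With k = 3, power is then 40% v 65%, 26% v 71% and 17% v 75%.

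**4. Haemophilia comparison.** Further assumptions: 200 haemophilia patients, 5% women there against 50% in the rare-disorder group.

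*True difference, 64 v 200, Fisher against stratified Wilcoxon:* 77% v 62% (4 v 6, k = 1.5), 93% v 87% (4 v 6, k = 3), 70% v 93% (8 v 12, k = 3). Over all settings the result ran from about 16 points in Fisher's favour to about 25 against.

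*No within-sex difference, 64 v 200:* Fisher on the cut rejects in 9–16% of runs, an unstratified Wilcoxon on the full score in 10–16%, and the sex-stratified test in 4–5%. The excess shrinks with a smaller rare-disorder group; for Fisher it falls to about 6% at the low end.

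*Why.* Take male mean 4, female mean 5, k = 3 in both groups. The negative binomial gives P(score ≥3) = 0.63 for men and P(score ≥5) = 0.475 for women. Share abnormal: rare disorders 0.5 × 0.63 + 0.5 × 0.475 ≈ 55%; haemophilia 0.95 × 0.63 + 0.05 × 0.475 ≈ 62%. Mean score: 0.5 × 4 + 0.5 × 5 = 4.5 against 0.95 × 4 + 0.05 × 5 = 4.05. The cut makes the rare disorders look milder and the unstratified score makes them look worse, although bleeding is identical within each sex.

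**The case against.** The strongest reply is that the plan does not require the cut. It is conditional, tests for an uncut score stand in the same section, and section 7.1 keeps the score numeric for description. The cut also has a natural home in section 7.2, where NHA accuracy is judged against ISTH-BAT. This stands. A reader might infer from "Fisher's exact test for categorical variables" that bleeding-score comparisons are bound for Fisher's test, but the text only permits that route. What remains is that no sentence says which route is taken.

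Second, the only bleeding-score group comparison listed as an objective is the one with haemophilia, and there the power loss is not established: Fisher's test can even appear stronger. This also stands, so the 10 to 60 points cannot be carried over to it. Part of that apparent strength, however, is the sex-mix effect, since Fisher's test also rejects too often when nothing differs within sex.

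Third, severity above the limit is recorded elsewhere, in the RBD bleeding score (for which section 7 gives no cut) and in the four-level severity grade. It would therefore be wrong to say that such differences become invisible to the study. They are lost only to a test on the cut ISTH-BAT.

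Fourth, the study is exploratory and sets no power target. No design power is missed; the loss is one of information. Because recruitment cannot be extended, that still matters.

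**Conclusion.** The point holds as a cheap improvement, not as an error in a stated analysis. The plan fixes neither the scale nor the handling of sex for ISTH-BAT group comparisons, and the routes it leaves open perform worse than an available alternative.

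For groups with a similar sex mix, testing the cut score costs roughly 10 to 60 points of power. That range rests on assumed score distributions, a 1.5-fold difference in means or d = 0.5, and Table 3 counts × 70%. It persists at the smaller sizes expected if children have only iCHEC.

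For haemophilia A/B, the power difference has no fixed sign. The firmer problem there is sex confounding on both permitted scales: about 9 to 16% rejections with no within-sex difference, against about 5% with stratification. This depends on the assumed 50% v 5% women, women's means 1.25 times men's, and 64 v 200 patients. None of these is in the documents, and with an equal sex mix the excess would not arise.

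**What to change.** Add to section 7, and refer to it for the haemophilia comparison in section 7.2, wording such as: *Between-group comparisons of the ISTH-BAT score are made on the full numeric score, using a sex-stratified Wilcoxon (van Elteren) test or a proportional-odds model with sex as covariate. The median difference or common odds ratio is reported with its 95% CI. The sex-specific normal/abnormal classes are used for descriptive percentages with 95% CI and, where needed, for the NHA diagnostic-accuracy analysis.* One of the two methods should be named before the data are analysed.

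The cost is one or two sentences and no new data. The percentage abnormal, which is easy to read, is still reported but is no longer the tested outcome. If the haemophilia group contains few women, the stratified comparison will rest mainly on men, and the report should say so.

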1.2. Clinical manifestations

Patients affected by rare bleeding disorders have a wide spectrum of clinical presentations that varies from a mild or moderate bleeding tendency to potentially serious or life-threatening haemorrhages [11].

Occasionally, the interplay with other inherited coagulation disorders such as platelet defects, von Willebrand disease and other coagulation factor deficiencies may give a more severe bleeding tendency [12-18].

There is a heterogeneous association between coagulation factor activity level and clinical bleeding severity in the different rare bleeding disorders. The coagulation factor activity levels that are necessary for patients to remain asymptomatic are [19]:

- Fibrinogen: > 100 mg/dL;
- FV: 12%;
- FV & VIII: 43%;
- FVII: 25%;
- FX: 56%;
- FXI: 26%;
- FXIII: 31%

Coagulation factor activity levels that corresponded with spontaneous major bleeding were [19]:

- Fibrinogen: undetectable levels;
- FV: undetectable levels;
- FV & VIII: 15%;
- FVII: 8%;
- FX: 10%;
- FXI: 25%;
- FXIII: undetectable

For the fibrinolysis disorders, there are no data available on the factor activity levels necessary to remain asymptomatic. Available data on patients with rare bleeding disorders are based on clinical records, which will predominantly include patients presenting with more severe bleeding symptoms. This generates a high risk of ascertainment bias, with a possible overestimation of the severity of bleeding in both homozygous and heterozygous individuals at group level.

Fibrinogen disorders

Afibrinogenemia (defined as fibrinogen <200 mg/L) is inherited in an autosomal recessive pattern. Patients with congenital afibrinogenemia suffer from a lifelong severe bleeding, with haematomas, haematemesis, melaena, or umbilical cord bleeding manifesting in the newborn period in severe cases [20]. Internal bleeding and spontaneous splenic rupture are common features, as is severe bleeding after minor trauma, easy bruising and gingival haemorrhage. In a study from 1971 that described all known case-reports of afibrinogenemia up to that time (n=23) 52% of patients reported umbilical bleeding, 70% severe bleeding after minor traumata and 13% central nervous system bleeding [21]. Arterial and venous thromboembolic complications were also recorded in some cases, as well as recurrent miscarriage [22].

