1.6. Management

Many patients and bleeding episodes will not require therapy: in a North-American registry study in 294 patients with a rare bleeding disorder half of all bleeding episodes did not require therapy [11]. On the other side of the treatment spectrum are patients with severe FX and FXIII deficiency, who may require lifelong prophylaxis treatment. If treatment is needed, the optimal treatment is often unknown as high-quality evidence is lacking. Both factor replacement therapy and non-transfusional treatment are available at present. The backbone of treatment is factor replacement, either in the form of recombinant factor, factor concentrate, prothrombin complex concentrate or plasma products (in order of preference and depending on availability). Non-transfusional treatment includes antifibrinolytic agents (tranexamic acid or ϵ -aminocaproic acid), which can be used as a supplement to factor replacement in major bleedings, and instead of replacement therapy in minor bleeding. Treatment-related complications have been reported and include viral seroconversion, anaemia, allergic reactions and venous access device-related events [11]. Cases of inhibitors to FV and FXI have been reported.

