6. METHODS

6.1. Study procedures

Patients will be approached by their own treating physician. Data will be collected through questionnaires, a clinical interview, a blood and saliva sample obtained from each participant, and thorough review of electronic patient records. An overview of study procedures is given in Table 4. All procedures are study related. In case a physician visit with the treating physician is already planned, or in case a venepuncture for regular diagnostics or treatment is already planned, this can be combined with the study procedures to prevent an extra visit.

Table 4 Overview of study procedures for each adult subject

Procedure	Outcome
Study physician visit	

 Clinical interview 	
 Bleeding score (ISTH-BAT) RBD bleeding score[52] Children: iCHEC
Questionnaires	

 Self-administered 	
 Demographic characteristics (generic) Socio-economic characteristics (generic) Clinical characteristics (bleeds, treatment), HIV status (patients born before 1985) and hepatitis C status (patients born before 1992) Medical history (generic) Sexuality (generic) General health status (Rand-36/Cho-KLAT) Sports and physical activity (MAQ/HeptestQ) Adherence (VERITAS-pro) Pain (generic) Needle phobia (generic) Experience with care (generic)
Electronic patient records	
	
 Date of birth Sex Baseline factor activity level Baseline factor antigen level Treatment type (prophylactic treatment or on-demand treatment) Body weight and height Bleeding score at diagnosis Relevant previous medical history, i.e. arterial thrombosis, atherosclerosis, medication use, pregnancies and outcomes
Blood samples: 72-83 ml	

 Haemostasis 	
 Screening tests - PFA - Haemoglobin

		
 - Thrombocytes - VWF ristocetin cofactor - VWF antigen - VWF collagen binding assay - FVIII act one stage - FVIII chromogen - aPTT - PT - Fibrinogen - Thrombin time 	
 - Leucocytes & differentiation - Peripheral blood smear - Creatinine - ALAT - TSH - D-dimer - Antitrombin - Protein C - Protein S - TFPI
	
 • Diagnostic tests 	
 - FII - FV - FVII - FIX 	
 - FX - FXI - FXII - FXIII

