7.1. Primary objectives

- *Describe the epidemiology, clinical presentation, bleeding score, bleeding episodes, quality of life, laboratory parameters, genetics and treatment of homozygous and known heterozygous individuals (of all ages) with rare bleeding disorders (disorders of fibrinogen, FII, FV, FV & VIII, FVII, FX, FXI, FXIII and alpha-2-antiplasmin and PAI-1 deficiency) in the Netherlands;*

We will use descriptive statistics using means, SD and medians. Interquartile ranges will be used when appropriate. Prevalence will be reported with 95% confidence intervals.

- *Examine the relationship between clinical and laboratory presentation (clinical and laboratory phenotype), and between phenotypes and genetics (genotype);*

Descriptive statistics will be used. Regression analysis will be used to determine the association between coagulation factor activity level (dependent variable) and clinical

bleeding severity as a continuous variable (independent variable), with adjustment for age at data collection, sex, etcetera.

- *Examine the relationship between quality of life, phenotype and genotype;*
Descriptive statistics will be used. Regression analysis will be used to determine the association between quality of life (dependent variable) and clinical bleeding severity or coagulation factor activity level as a continuous variable (independent variable), with adjustment for age at data collection, sex, etcetera.
- *Validate the established factor activity levels for patients to remain without symptoms.*
Descriptive statistics will be used.

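### The asymptomatic grade takes no account of prophylaxis, so any never-bled patient on prophylaxis would distort the symptom-free-level check in small disorder groups

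*Combined protocol and SAP*

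**What the plan says.** Section 7 adopts a four-level clinical bleeding severity scale from a cited European network study. The lowest level is "Asymptomatic: no documented bleeding episodes". Neither a look-back period nor a treatment condition is attached. The top level, Grade III, includes "haemarthrosis, bleeding of the central nervous system, the umbilical cord or the gastrointestinal tract".

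Section 7.1 then uses the grade in three places:
- Factor activity level is regressed on severity, "with adjustment for age at data collection, sex, etcetera".
- Quality of life is regressed on "bleeding severity or coagulation factor activity level as a continuous variable (independent variable"), with the same open-ended adjustment.
- The objective "Validate the established factor activity levels for patients to remain without symptoms" is addressed by descriptive statistics only.

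The levels to be checked are in section 1.2, introduced by "The coagulation factor activity levels that are necessary for patients to remain asymptomatic are": 56% for FX and 31% for FXIII, among others. The same section gives the levels that went with spontaneous major bleeding: 10% for FX and undetectable for FXIII.

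The protocol expects prophylaxis. Section 1.6 refers to "patients with severe FX and FXIII deficiency, who may require lifelong prophylaxis treatment". Table 4 in section 6.1 takes "Treatment type (prophylactic treatment or on-demand treatment") from the records, along with baseline factor activity level and the bleeding score at diagnosis. Section 6.2 gives prophylaxis users their own adherence questionnaire.

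**The concern.** Prophylaxis is given because of low levels and severe disease, and its purpose is to suppress bleeding. Under the stated rule, a patient treated from before a first bleed, for example after a sibling's diagnosis, falls in the same grade as someone who has never needed treatment. In the symptom-free-level check that patient counts as symptom-free at a near-zero level, when treatment is the reason for the absence of bleeding. In the level-severity regression the same patient places a very low level at grade 0 and flattens the slope.

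The symptom-free levels are listed factor by factor, so the check has to be read within disorders, and some of those groups are very small. Quality of life has a related mismatch: it is measured under current treatment, while severity appears to be lifetime history.

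**Working it through.** The plan states no figure on this point, so there is nothing to reproduce. The check asks how far one or two such patients would move the results.

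**Expected participants.** Table 3 lists 337 known patients, of whom 10 have FX and 16 have FXIII deficiency. Section 5.1 expects 70% response: 0.70 × 337 = 236; 0.70 × 10 = 7; 0.70 × 16 = 11.2, about 11.

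**Levels.** Untreated levels are set on a straight line from the section 1.2 symptom-free level (grade 0) to the level for spontaneous major bleeding (grade III): FX 56% to 10%, FXIII 31% to 0%. The slope with nobody misplaced is (10 − 56)/3 = −15.3 points per grade for FX and (0 − 31)/3 = −10.3 for FXIII.

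**Assumptions.** The grade mix and the number misplaced are not in the documents. Two mixes are used per disorder, with the non-severe patients spread over grades 0, 1 and 2. One or two grade III patients are then moved to grade 0 while keeping their untreated level.

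| Group | Severe / truly asymptomatic | Moved | Mean level in asymptomatic group | Slope | Slope left |
|---|---|---|---|---|---|
| FX, n = 7 | 4 / 1 | 1 | (56 + 10)/2 = 33.0 | −8.4 | 55% |
| FX, n = 7 | 2 / 2 | 1 | (2×56 + 10)/3 = 40.7 | −9.6 | 63% |
| FXIII, n = 11 | 6 / 2 | 1 | (2×31 + 0)/3 = 20.7 | −7.4 | 72% |
| FXIII, n = 11 | 6 / 2 | 2 | (2×31 + 0)/4 = 15.5 | −5.5 | 53% |
| FXIII, n = 11 | 3 / 3 | 1 | (3×31 + 0)/4 = 23.25 | −7.6 | 74% |
| FXIII, n = 11 | 3 / 3 | 2 | (3×31 + 0)/5 = 18.6 | −5.2 | 50% |

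The slope is the least-squares value Sxy/Sxx. For the first row the grades are 0, 1, 2, 3, 3, 3, 0 and the levels 56, 40.67, 25.33, 10, 10, 10, 10. Then Sxx = 32 − 12²/7 = 11.43 and Sxy = 181.33 − 12×162/7 = −96.4. This gives −96.4/11.43 = −8.4, which is 55% of −15.3.

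**Pooled.** With 236 patients spread evenly over the four grades (59 each) and assumed levels of 50, 35, 20 and 5, moving 3, 6, 12 or 18 patients leaves 96%, 91%, 83% or 76% of the slope.

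**How many could be affected.** Cord bleeding is a newborn event and counts as Grade III, which points to a lifetime grade. A patient who bled before prophylaxis therefore keeps that grade. Section 1.2 reports cord bleeding in 73-80% of FXIII cases. On that symptom alone, 100 − 80 = 20% to 100 − 73 = 27% would escape Grade III, and some of those would have other bleeds. These are published case series and may be selected, so this is a rough guide. With nobody treated before a first bleed, the bias from this source is nil.

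**The case against.** The strongest reply has four parts.

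1. Treatment is not ignored. The first objective in section 7.1 describes it, and the adjustment list is left open, so treatment is unspecified rather than ruled out. This is right about the regressions. It does not reach the grade itself or the symptom-free-level check, which has no covariates.

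2. The grade reads as lifetime history, so the affected group is narrow and may be empty. This stands, and it sets the limit of the point.

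3. The symptom-free-level check is descriptive, with no threshold estimator to bias, and the study calls itself explorative. A never-bled prophylaxis patient could be noticed because treatment type is recorded. That holds only if someone tabulates by treatment, which the plan does not say it will do.

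4. Redefining the severity scale would weaken comparability, because the scale and the levels being checked are cited to the same source. Splitting quality of life by prophylaxis also conditions on a consequence of level and severity. Both objections stand. They are reasons to leave the scale alone and to keep the split supplementary.

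A reader might infer that every severely deficient patient kept bleed-free by prophylaxis is graded asymptomatic. The documents do not support that, since earlier bleeds appear to count. Nor do they support an assumption that a quarter to a half of severe prophylaxis patients would be regraded: no count is given, and the cord-bleeding figures for FXIII sit badly with one half.

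**Conclusion.** The point holds in a limited form. The rule would place a never-bled patient on prophylaxis in the asymptomatic group, and section 7.1 carries that grade into the symptom-free-level check and the level-severity regression. The direction is clear: the apparent symptom-free level falls and the relation weakens.

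The size depends on a number that the documents do not give. Within FX or FXIII, one such patient is enough to matter: under the mixes shown, the asymptomatic mean drops by about 15 to 23 points in FX (56 − 40.7 and 56 − 33.0) and by about 8 to 10 points in FXIII (31 − 23.25 and 31 − 20.7). Across all disorders the effect is small unless many patients are involved.

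These results assume straight-line levels, the stated grade mixes, 70% response in each disorder, and analysis of the untreated level. Factors are also assayed at the visit, and section 7 does not say which value is used.

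A reader might also infer that one bleed-free FXIII patient at about 0% contradicts the 31% level. It does not: one person cannot refute a group-level figure. Such a patient would be a misleading counter-example.

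**What to change.** In section 7, keep the cited severity scale, state that it is graded on lifetime bleeding, and state that the recorded baseline (untreated) factor level is the one analysed.

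In section 7.1:
- **Symptom-free levels:** report patients on prophylaxis with no documented bleed on a separate line for each disorder, and do not count them as asymptomatic.
- **Level-severity regression:** repeat it as a sensitivity analysis without these patients, or with the bleeding score at diagnosis. Leaving them out is the more direct choice, since a patient diagnosed through the family before any bleed would also score low at diagnosis.
- **Quality of life:** report the regression additionally by treatment type, labelled supplementary.

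No new data field is needed, because treatment type, baseline level and bleeding score at diagnosis are already in Table 4. The cost is some analysis wording and a little extra analysis. The downside is that a few of the lowest-level patients leave the symptom-free-level check. Setting the rule before the data are seen also avoids a choice made in the light of the results.
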